- When several toxicities with different grades of severity occur at the same time, appropriate action should be made according to the highest grade observed.
- If, in the opinion of the investigator, a toxicity is considered to be due solely to MGC018 and is of sufficient grade to warrant treatment delay, therapy should be delayed and omitted until resolution of toxicity.
- If, in the opinion of the investigator, a toxicity attributed to MGC018 is of sufficient grade to warrant permanent discontinuation of therapy, therapy should be permanently discontinued.

For patients who require a dose-reduction, the first reduction would be to 1.5 mg/kg every 28 days with a second reduction to 1.0 mg/kg every 28 days, as needed (**Table 4**).

Table 4. Dose levels of MGC018

| Dose levels | MGC018 |
|-------------------------|---------------|
| Level 1 (starting dose) | 2.0 mg/kg Q4W |
| Level -1 | 1.5 mg/kg Q4W |
| Level -2 | 1.0 mg/kg Q4W |

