4.2.3.2 Guidelines for management of suspected MGC018-related toxicities

Criteria for treatment modification and guidelines for the management of toxicities are summarized below. Generally, temporary suspension of MGC018 must occur if a patient experiences a serious adverse event or a grade 3 or 4 non-serious adverse event assessed by the investigator as related to MGC018. If the event resolves to grade ≤ 1 , MGC018 may be restarted at the same dose level. If MGC018 is delayed due to toxicity for > 8 weeks beyond when the next dose should have been given, the patient must be permanently discontinued from MGC018.

PULMONARY EVENTS

Immune-mediated pulmonary events are a potential risk with MGC018. Patients will be assessed for pulmonary signs and symptoms throughout the study and will have computed tomography (CT) scans of the chest performed at every tumor assessment.

All pulmonary events should be thoroughly evaluated for other commonly reported etiologies such as pneumonia or other infection, lymphangitic carcinomatosis, pulmonary embolism, heart failure, chronic obstructive pulmonary disease, or pulmonary hypertension. Management guidelines for pulmonary events are provided in Table 5.

Table 5. Management Guidelines for Pneumonitis

| Event | Management |
|--------------|---|
| Grade 1 | 
 • Continue MGC018 and monitor closely. • Re-evaluate on serial imaging. • No specific therapy required |
| Grade 2 | 
 • Hold MGC018 • Consider treatment with corticosteroids equivalent to 1–2 mg/kg/day oral prednisone or equivalent divided twice daily • Taper corticosteroids over 4 weeks or as clinically indicated • Resume MGC018 administration at next scheduled dose if pneumonitis resolves to grade 1 or baseline within 5 days with or without treatment. On resuming MGC018, reduce dose by one dose level. • Discontinue MGC018 after second occurrence |
| Grade 3 or 4 | 
 • Permanently discontinue MGC018 • Hospitalize • Referral for pulmonary consult with diagnostic evaluation with chest X-ray and CT scan. • Initiate treatment with IV corticosteroids, suggest methylprednisolone at 2 to 4 mg/kg/day divided twice daily. Higher doses may be used in consultation with the sponsor's medical monitor. • If event does not improve within 3 to 5 days after initiating corticosteroids, consider adding an immunomodulatory agent. |

HEPATIC EVENTS

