|--------------------|--|
| Nephritis, Grade 3 | 
 • Consider hospitalization, nephrology consultation, and renal biopsy to confirm interstitial nephritis. • Initiate treatment with corticosteroids equivalent to 2–4 mg/kg/day IV methylprednisolone divided twice daily. Taper corticosteroids over 4 weeks or as clinically indicated. • On resuming MGC018, reduce dose by one dose level after first and second occurrences • Discontinue MGC018 after third occurrence |
| Nephritis, Grade 4 | 
 • Treat as grade 3 • On resuming MGC018 reduce dose by two dose levels after first occurrence • Discontinue MGC018 after second occurrence |

ENDOCRINE EVENTS

Endocrine events are a potential risk with MGC018.

Thyroid disorders may occur at any time during treatment with MGC018. Monitor participants for changes in thyroid function per protocol and as indicated based on clinical evaluation and for clinical signs and symptoms of thyroid disorders. Isolated hypothyroidism may generally be managed with replacement therapy without treatment delay and without corticosteroids.

Management guidelines for endocrine events are provided in Table 11.

Table 11. Management Guidelines for Endocrine Events

| Event | Management |
|-----------------------------|---|
| Hyperthyroidism, Grade 1 | 
 • Continue MGC018 • No specific therapy required |
| Hyperthyroidism, Grade 2 | 
 • Hold MGC018 • Consider starting oral corticosteroid therapy. • Short course of corticosteroid such as methylprednisolone 1 to 2 mg/kg IV (or equivalent) divided twice daily. • Resume MGC018 if corticosteroid if corticosteroid dose is reduced to ≤ 10 mg prednisone or equivalent per day and stable on hormone replacement therapy (if necessary). • No dose reduction required after first occurrence • On resuming MGC018, reduce dose by one dose level after second and third occurrences • Discontinue MGC018 after fourth occurrence |

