4.4 STUDY ASSESSMENTS

The schedule of activities to be performed during the study is provided in Appendix 1. All activities must be performed and documented for each patient. Patients will be closely monitored for safety and tolerability throughout the study. Patients should be assessed for toxicity prior to each dose; dosing will occur only if the clinical assessment and local laboratory test values are acceptable.

All treatment visits must occur ± 3 days from the scheduled date unless otherwise noted (see Appendix 1). All assessments should be performed on the day of the specified visit unless a time window is specified. Patients must be assessed for toxicity prior to each dose; dosing will occur only if the clinical assessment and local laboratory test values are acceptable. Assessments scheduled on the day of study treatment administration should be performed prior to dosing, unless otherwise specified.

Laboratory tests performed within 14 days of Day 1 of Cycle 1 and within 3 days of Day 1 of subsequent cycles do not need to be repeated prior to therapy administration.

If a holiday, weekend, or other event precludes scheduled dosing, dosing may be postponed to the soonest following date, with subsequent dosing continuing on a 28-day schedule. If treatment is postponed for fewer than 3 days, the patient can resume the original schedule.

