4.4.6 Laboratory, biomarker, and other biological samples

Samples for the following laboratory tests must be reviewed prior to dosing. See Appendix 1 for specifics related to which lab tests are required at specific time points during study ("screening" vs "on treatment", etc.):

- Hematology: WBC count, RBC count, hemoglobin, hematocrit, platelet count, and differential count (neutrophils, eosinophils, basophils, monocytes, lymphocytes, other cells).
- Chemistry panel (serum or plasma): bicarbonate or total carbon dioxide (if considered standard of care for the region), sodium, potassium, chloride, glucose, BUN or urea, creatinine, total protein, albumin, phosphorus, calcium, total bilirubin, alkaline phosphatase, ALT, and AST.
- Coagulation: INR, and aPTT (screening only).
- Thyroid function testing: thyroid-stimulating hormone (TSH), free triiodothyronine (T3) (or total T3 for sites where free T3 is not performed), and free thyroxine (also known as T4) at screening only. Repeat thyroid function testing as clinically indicated.

- Pregnancy test

All women of childbearing potential will have a serum pregnancy test at screening, and during the study, urine pregnancy tests will be performed at every cycle and after study treatment is discontinued. If a urine pregnancy test is positive, it must be confirmed by a serum pregnancy test.

A woman is considered to be of childbearing potential if she is postmenarchal, has not reached a postmenopausal state (≥ 12 continuous months of amenorrhea with no identified cause other than menopause), and has not undergone surgical sterilization (removal of ovaries and/or uterus).

The following samples will be sent to the PI or a designee for analysis or banked for subsequent analysis:

- Peripheral blood to be obtained on day 1 of cycle 1, day 1 of cycle 3, and at progression
- Prior to treatment initiation, tumor tissue will be obtained following progression on most-recent therapy for determination of biomarker status including exploratory correlative analyses. Please refer to the lab manual for details. **If a biopsy is not feasible and/or safe, it may be waived after discussion with the principal investigator.** In this case, we will obtain archival tissue if available.

For sampling procedures, storage conditions, and shipment instructions, see the laboratory manual.

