4.5 TREATMENT, PATIENT, AND STUDY DISCONTINUATION

4.5.1 Treatment discontinuation

Patients must permanently discontinue study treatment if they experience any of the following:

- Intolerable toxicity related to study treatment, determined by the investigator to be unacceptable given the individual patient's potential response to therapy and severity of the event
- Any medical condition that may jeopardize the patient's safety if he or she continues study treatment
- Investigator determines it is in the best interest of the patient
- Use of another non-protocol anti-cancer therapy
- Pregnancy

- Loss of clinical benefit as determined by the investigator after an integrated assessment of radiographic and biochemical data, local biopsy results (if available), and clinical status (e.g., symptomatic deterioration such as pain secondary to disease)
- Radiographic disease progression per RECIST v1.1 or symptomatic deterioration attributed to disease progression

In select scenarios, patients may continue therapy in setting of radiographic progression and ongoing clinical benefit, as assessed by investigator. In this scenario, medical interventions such as stereotactic radiosurgery (SRS) and stereotactic body radiation therapy (SBRT) to isolated sites of disease progression in the setting of otherwise ongoing treatment response will be allowed on a case-by-case basis with PI approval.

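### Grade 2 hyperthyroidism: the restart rule tests steroid dose and hormone replacement but not the hyperthyroidism, so it permits a same-dose restart while grade 2 toxicity is still active

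*Combined protocol and SAP*

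**What the plan says.** The grade 2 hyperthyroidism row of Table 11 (section 4.2.3.2) orders a hold, asks the investigator to consider oral steroids, mentions a short methylprednisolone course, and then gives the restart rule: "Resume MGC018 if corticosteroid if corticosteroid dose is reduced to ≤ 10 mg prednisone or equivalent per day and stable on hormone replacement therapy". A parenthesis limits the replacement condition to patients who need it. The row requires no dose reduction at a first occurrence and a one-level reduction after the second and third.

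The text above Table 11 links replacement to an underactive thyroid: "Isolated hypothyroidism may generally be managed with replacement therapy without treatment delay and without corticosteroids". It also says: "Monitor participants for changes in thyroid function per protocol and as indicated based on clinical evaluation and for clinical signs and symptoms of thyroid disorders".

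Four general provisions bear on the same decision:

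- **Section 4.2.3.1:** if the investigator considers a toxicity to be "due solely to MGC018 and is of sufficient grade to warrant treatment delay, therapy should be delayed and omitted until resolution of toxicity".
- **Section 4.2.3.2, opening paragraph:** "temporary suspension of MGC018 must occur if a patient experiences a serious adverse event or a grade 3 or 4 non-serious adverse event" that the investigator judges related to MGC018. Restart is then allowed on return to grade 1 or lower, and a delay of more than 8 weeks past the due dose ends treatment.
- **Section 4.4:** patients are assessed for toxicity before each dose, and "dosing will occur only if the clinical assessment and local laboratory test values are acceptable".
- **Section 4.5.1:** treatment stops permanently for "Any medical condition that may jeopardize the patient's safety if he or she continues study treatment".

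On testing, section 4.4.6 lists TSH, T3 and "free thyroxine (also known as T4) at screening only. Repeat thyroid function testing as clinically indicated".

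**The concern.** A hold should end when the reason for it has gone or is under control. Here the two release conditions describe treatment, not the event. Steroid dose says what the patient is taking. Replacement stability concerns a patient who has become hypothyroid, and it drops out for anyone who needs no replacement. The row can therefore order a hold and release it with nothing about the hyperthyroidism having changed.

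This is a patient-safety matter and a matter of consistency between sites. One site may follow the specific row and restart at the same dose. Another may follow the general note in section 4.2.3.1 and wait. The Simon design and the analysis of ORR are not affected.

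**Working it through.** The plan states no figure on this point, so the check is a comparison of texts with a count.

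**1. Apply the row to a patient.** Take a first, non-serious grade 2 hyperthyroidism in a patient who needs no hormone replacement.

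- Steroid condition: met on the day of the hold if no steroid is given, since oral steroids are only to be considered. If the short course is given, it is met once the dose falls to 10 mg/day or less.
- Replacement condition: does not apply.
- Hyperthyroidism grade or control: not asked.
- Dose on restart: unchanged.

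Every written restart condition in the row is met with the event still at grade 2.

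**2. Compare with the grade 3 row of the same table.** That row allows restart to be considered on full resolution, or a stable state on replacement, within 28 days, plus the same steroid limit. A grade 3 patient who needs no replacement must therefore show full resolution. A grade 2 patient in the same position has no recovery test to pass.

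**3. Count the comparable rows.** These are the grade 2 rows in Tables 5 to 18 (numbered as in the body of the document) that order MGC018 to be held.

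| What restart or stopping depends on | Rows | Count |
|---|---|---|
| Restart tied to grade 1 or lower, or baseline | pneumonitis, bilirubin, diarrhea or colitis, nephritis, blepharitis, thrombocytopenia, pleural effusion, pericardial effusion, nervous system, musculoskeletal | 10 |
| Restart tied to control of the event | hypophysitis | 1 |
| Only a stopping rule tied to recovery (21 days) | transaminases | 1 |
| Neither | hyperthyroidism | 1 |

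10 + 1 + 1 + 1 = 13, and 1/13 = 7.7%.

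**4. Look for a general rule that supplies the missing test.**

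- The grade 1 restart rule at the start of section 4.2.3.2 follows serious or grade 3 to 4 events. It does not reach a non-serious grade 2 event.
- Section 4.2.3.1 does say to wait for resolution, but only when the investigator attributes the toxicity solely to MGC018, and it is worded as a recommendation.
- Section 4.4 sets a check before every dose but gives no thyroid criterion. The study calendar in Appendix 1 schedules blood counts and chemistries on treatment, and its chemistry list contains no thyroid test. Thyroid values enter the check only if the investigator orders them.
- Section 4.5.1 turns on the investigator's view of jeopardy.
- The 8-week rule limits how long a hold can last: 28 + 8 × 7 = 84 days after the previous dose. It sets no condition for ending the hold early. Because it exists, the row's lack of its own day limit is not counted as a fault; the diarrhea and hypophysitis rows set none either.

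**5. How often the row might be used.** The readable text gives no rate. For an assumed per-patient risk p of grade 2 hyperthyroidism and n = 17, the expected number is 17p and the chance of at least one case is 1 − (1 − p)^17.

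| Assumed p | Expected cases | Chance of at least one |
|---|---|---|
| 1% | 0.17 | 15.7% |
| 5% | 0.85 | 58.2% |
| 10% | 1.70 | 83.3% |

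These values only illustrate scale and are not evidence about this drug. They give the chance that the row is used at all. The chance of a restart with active toxicity is lower, because it also needs the steroid and replacement conditions to be met, persistence at grade 2 when the next dose is due, and an investigator who finds dosing acceptable.

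**The case against.** The strongest reply is that the protocol already contains a resolution rule. The hold itself shows that grade 2 hyperthyroidism warrants delay, MGC018 is the only investigational product, and Table 11 sits under suspected MGC018-related toxicities, so section 4.2.3.1 would often apply and call for waiting. In addition, the pre-dose check in section 4.4 is mandatory, and grading and attribution rest on the investigator in every row. This stands in part, and it is why the row can be said only to permit a restart. The gap remains for events not attributed solely to MGC018, and for a site that takes the specific row as overriding a general note.

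Second, the row can be read as requiring a stable patient, on replacement if needed. The grade 3 hyperthyroidism row also mentions starting replacement as necessary, so replacement is not foreign to this event. But a stable grade 2 event is still grade 2. If replacement stability is credited as control, it covers only patients who need replacement.

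Third, the count depends on classification. The transaminase row also sets no recovery test on restart itself; judged on restart alone, 2 of 13 rows (15.4%) lack one. That is correct. The transaminase row does, however, end treatment if grade 1 or baseline is not reached in 21 days. For an event found at a pre-dose check, that falls before the next scheduled dose 28 days later. The hyperthyroidism row has no such stop.

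Finally, the repeated words in the restart sentence suggest a drafting slip, not a decision to dose through toxicity. That may well be so, and it makes correction easier. Sites will still apply the text as printed.

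**Conclusion.** The concern holds. As written, the grade 2 hyperthyroidism row allows MGC018 to restart at the same dose, at a first occurrence, with grade 2 toxicity still active. This applies to a patient on at most 10 mg/day of prednisone equivalent who needs no replacement. It is the only one of 13 grade 2 hold rows that ties neither restart nor stopping to recovery or control. That classification involves judgement, but for patients who need no replacement the result is the same on either reading of the stability wording.

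The general rules make such a restart less likely without ruling it out. How often the row would be used cannot be estimated from the documents. This should be corrected at the next amendment on safety and consistency grounds; it has no bearing on the primary analysis.

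**What to change.** Replace the restart line in the grade 2 hyperthyroidism row of Table 11 with wording such as:

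> Restart MGC018 only when (a) hyperthyroidism is at grade 1 or lower or at baseline, or is controlled, meaning symptoms at grade 1 or lower on treatment, confirmed by repeat thyroid function tests; (b) steroids are at or below 10 mg/day prednisone equivalent; and (c) a patient who has become hypothyroid is stable on replacement.

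Accepting control as well as resolution keeps chronic but managed thyroid disease from blocking treatment. No new day limit is needed, because the 8-week rule in section 4.2.3.2 already applies.

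The cost is a wording change in one row and one thyroid blood test before restart for each affected patient. That makes mandatory, in this one situation, a test that section 4.4.6 leaves to clinical indication. The downside is that some patients may restart slightly later.

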| Hyperthyroidism, Grade 3 | 
 • Hold MGC018 • Consider hospitalization and consulting endocrinologist • Begin IV corticosteroids such as methylprednisolone 2 to 4 mg/kg IV (or equivalent) divided twice daily. • Initiate hormonal replacement therapy as necessary • Consider restarting MGC018 with complete resolution or stable on hormone replacement therapy within 28 days and if corticosteroid dose is reduced to ≤ 10 mg prednisone or equivalent per day. • On resuming MGC018, reduce dose by one dose level after first and second occurrences • Discontinue MGC018 after third occurrence |
| Hyperthyroidism, Grade 4 | 
 • Treat as grade 3 • On resuming MGC018 reduce dose by two dose levels after first occurrence • Discontinue MGC018 after second occurrence |

| Event | Management |
|--------------------------|---|
| Hypophysitis, Grade 1 | 
 • No specific therapy required • Continue MGC018 |
| Hypophysitis, | 
 • Hold MGC018 |

| | |
|----------------|--|
| Grade \geq 2 | 
 • Consult endocrinologist • Consider hospitalization • Consider short course of high dose IV corticosteroids e.g. methylprednisolone 2 to 4 mg/kg/day or equivalent divided twice daily. • Initiate hormonal replacement as indicated • Study drug may be resumed as allowed by protocol when: 
 • Endocrinopathy is controlled with appropriate replacement therapy • Corticosteroid dose reduced to \leq 10 mg prednisone or equivalent per day. • Brain MRI recommended |
|----------------|--|

MRI = magnetic resonance imaging

OCULAR EVENTS

Ocular toxicity, including, but not limited to, dry eye, photophobia or blurry vision have been observed in participants treated with antibody drug conjugates, and could occur at any time during treatment with MGC018. Management guidelines for ocular events are provided in Table 12.

Table 12. Management Guidelines for Blepharitis

| Event | Management |
|----------------------|---|
| Blepharitis, Grade 1 | 
 No specific therapy required. Daily cleansing with warm, clean cloth. Apply lubricating eye drops Patient referral to ophthalmologist is strongly recommended. Initiate treatment with topical corticosteroid eye drops and topical immunosuppressive therapy. If symptoms persist, treat as a Grade 2 event. |

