| Blepharitis, Grade 2 | 
 Hold MGC018 Consider topical/ocular corticosteroids, antihistamine, artificial tears Resume MGC018 if resolved to \leq grade 1 within 28 days and discontinue MGC018 if symptoms last > 28 days On resuming MGC018, if symptoms lasted > 14 days, reduce dose by one dose level |
| Blepharitis, Grade 3 | 
 Hold MGC018 Consider referral to ophthalmologist. Consider topical/ocular and/or systemic corticosteroids Resume MGC018 if resolved to \leq grade 1 within 28 days and discontinue MGC018 if symptoms last > 28 days On resuming MGC018, reduce dose by one dose level |
| Blepharitis, Grade 4 | 
 Permanently discontinue MGC018 Consult ophthalmology within 24 hours Treat as for grade 3 and as appropriate for life-threatening symptoms |

HEMATOLOGIC EVENTS

Blood counts should be monitored to determine if dose modification is needed. Consider monitoring CBC bi-weekly or weekly based on the participant's medical history and incidence of myelosuppressive AE's during study drug administration.

Blood counts will be performed in case of fever (a measured temperature of 100.4 F or greater) or evidence of infection. Neutropenic complications should be managed promptly with antibiotic support and use of G-CSF according to current ASCO guidelines for use of white blood cell growth factors.

Consider transfusion of platelets for thrombocytopenia. Use of anticoagulants and platelet inhibitors should be held until thrombocytopenia resolves.

Anemia should be evaluated and treated for other underlying etiology e.g. iron or vitamin B12 deficiency, bleeding, and renal insufficiency. Consider transfusion of red blood cells or whole blood for

anemia. Caution is recommended in patients with \geq grade 2 anemia, with appropriate measures taken as clinically indicated. Patients will be supported appropriately by the treating physician.

No specific treatment or drug holds are required for lymphopenia, regardless of CTCAE grade, unless associated with opportunistic infection. If the patient develops an opportunistic infection with concurrent lymphopenia, MGC018 should be delayed until resolution of lymphopenia and the opportunistic infection

Management guidelines for hematologic events are provided in Table 13.

Table 13. Management Guidelines for Hematologic Events

| Event | Management |
|------------------------------|--|

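### The blepharitis guidance (Table 12) contradicts itself at grade 1, and sends persistent grade 1 events to a hold whose resume and stop tests do not work for them

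*Combined protocol and SAP*

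**What the plan says.** The ocular part of Section 4.2.3.2 refers all ocular events to Table 12, which is titled for blepharitis and graded 1 to 4.

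- **Grade 1.** The row starts "No specific therapy required. Daily cleansing with warm, clean cloth" and adds lubricating drops. It then states "Patient referral to ophthalmologist is strongly recommended" and continues "Initiate treatment with topical corticosteroid eye drops and topical immunosuppressive therapy. If symptoms persist, treat as a Grade 2 event". It says neither to hold nor to continue MGC018.
- **Grade 2.** MGC018 is held. Eye treatment is worded "Consider topical/ocular corticosteroids, antihistamine, artificial tears". No referral and no immunosuppressive is named. MGC018 resumes if the event has come down to "grade 1 within 28 days and discontinue MGC018 if symptoms last > 28 days". On resuming, the dose drops one level if symptoms lasted more than 14 days.
- **Grade 3.** MGC018 is held. The row says "Consider referral to ophthalmologist" and "Consider topical/ocular and/or systemic corticosteroids". The 28-day resume and stop wording is the same as for grade 2, and resumption is one dose level lower.

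**The concern.** There are two separate faults.

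First, one row tells the site both that no specific treatment is needed and that topical steroid and topical immunosuppressive treatment should be started. For topical treatment and referral, the grade 1 wording is also firmer than the wording for grades 2 and 3.

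Second, a grade 1 event that persists is moved to the grade 2 row. That row was evidently written for an event that starts above grade 1: it resumes on grade and stops on duration of symptoms. An event that never left grade 1 does not fit these tests.

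Section 5.1.1 lists ocular toxicity among the risks of MGC018, and Table 12 is the table to which the protocol sends sites for ocular events. Several centres will use it. Two of them could treat the same low-grade event differently, and could differ on whether MGC018 is held, resumed or stopped for good. That affects patient care, exposure and the recorded reasons for discontinuation.

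**Working it through.** The plan gives no figure on this point. The check compares the rows and works through the 28-day rule.

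**1. Grade 1 row.** The opening statement and the instruction to start treatment stand in the same row. The only conditional in the row is the one about persisting symptoms. It follows the treatment instruction and governs the move to grade 2. Nothing makes starting topical treatment depend on failure of cleansing or lubricants.

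**2. Strength of wording by grade.**

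| | Grade 1 | Grade 2 | Grade 3 |
|---|---|---|---|
| Topical steroid | start | consider | consider (topical and/or systemic) |
| Topical immunosuppressive | start | not named | not named |
| Ophthalmology referral | strongly recommended | not named | consider |
| MGC018 | no instruction | hold | hold |

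The wording weakens after grade 1 in the treatment and referral rows only. The drug hold goes the other way, and grade 3 adds systemic steroid as an option.

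**3. The 28-day rule for an escalated grade 1 event.** Let g be the day on which the event is at grade 1 or lower (g = 0 if it was never higher), and s the day on which symptoms end, with s ≥ g. The table does not say when the 28 days start, so a common start is assumed for both.

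- Resume test: g ≤ 28.
- Stop test, read literally: s > 28.
- Both hold whenever g ≤ 28 < s.

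Persistent grade 1 with symptoms to day 29: g = 0 and s = 29. Since 0 ≤ 28 and 29 > 28, both tests are met.

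Grade 2 improving to grade 1 on day 20, with symptoms to day 29: g = 20 and s = 29. Since 20 ≤ 28 and 29 > 28, both tests are met. The literal overlap is therefore not confined to escalated grade 1 events.

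Now read *symptoms* as symptoms above grade 1:

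- Stop test: g > 28.
- Resume (g ≤ 28) and stop (g > 28) are complementary, so the overlap is zero.
- For a persistent grade 1 event g = 0. Resume is true on the day the hold starts, and stop (0 > 28) is false for as long as the event stays at grade 1. The escalation has no effect.

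**4. Other tables.** For palmar-plantar erythrodysesthesia (28 days), grade 3 skin events (21 days) and grade 3 and 4 neutropenia (21 days), the same section judges resuming and stopping on one criterion, recovery to grade 1 or lower. Table 12 uses two.

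**The case against.** The strongest reply is that the grade 2 sentence is meant as two complementary branches: the event either comes down to grade 1 within 28 days or it does not. The protocol uses that structure elsewhere, and on that reading no event meets both tests. This stands, and a reader who infers that Table 12 necessarily orders both resumption and permanent discontinuation goes further than the text. But the complementary reading is not written, and it leaves the escalated grade 1 event with a hold that can be lifted at once. The path needs correction on either reading.

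A second reply is that the grade 1 row is a stepwise ladder: hygiene, lubricants, referral, topical treatment, then escalation. Bullet marks are missing from this table in the text available for review, so lost nesting cannot be excluded. No wording makes the treatment step conditional, however, and the two statements conflict in any layout.

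Third, rows for different grades do not contradict one another merely because one says start and another says consider. That is fair. A reader might infer that grade 1 is managed more intensively overall than grades 2 and 3. The documents do not support that, because grades 2 and 3 add a drug hold. The difference in wording is a reason to check the rows, not a second contradiction.

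Fourth, a reader might infer that the table offers a range of rival dosing outcomes for one event. Most of that range is a single sequence in time: no stated hold at first, a hold once symptoms persist, and a dose level on resuming that an explicit 14-day criterion decides. What is unclear is the resume and stop step, together with the undefined duration of persistence and start of the 28 days.

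**Conclusion.** The point holds as an internal inconsistency in Table 12. The grade 1 contradiction rests on the wording alone. The failure of the escalation path holds under both readings of *symptoms*: overlapping tests on the literal one, no effective exit test on the narrower one. The general suspension rule at the start of Section 4.2.3.2 does not settle it, because that rule covers serious or grade 3 or 4 related events.

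The size is limited. The readable documents give no incidence of blepharitis or of persistent grade 1 events, so no expected number of affected patients can be stated. A reader might infer that a wording-driven stop takes a patient out of a 17-patient trial. It does not: Section 6.2 analyses everyone who received at least one dose. Nor does the listing of ocular toxicity as an event of special interest raise the stakes for grade 1 blepharitis, since Section 5.2.3 covers grade 3 or higher. The two-stage design, its boundaries and its stated error rates are untouched. What remains is avoidable variation between sites in treating, holding and stopping the drug, which should be corrected. No view is taken on which clinical rule is right.

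**What to change.** Amend Table 12 as follows, with the content decided by the sponsor's medical lead:

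- Reconcile the grade 1 row so that it carries one instruction on treatment. If a stepwise approach is intended, write the conditions into the row.
- Check that the treatment and referral wording across grades 1 to 3 is what the sponsor intends.
- For grade 1 events escalated to the grade 2 row, state the resume and stop tests on one common criterion so that they are mutually exclusive. Define when symptoms count as persisting and when the 28 days start.
- Apply the same check to the 28-day sentence in the grade 2 and grade 3 rows, which share the wording.

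The cost is table wording in a protocol amendment. No change to the sample size or the statistical analysis is needed.
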